11.2 Early Termination or Suspension

Early Termination of the Study is the closure of a clinical study that occurs prior to meeting defined endpoints. This is possible for the whole study or a single site. Study Suspension is a temporary postponement of study activities related to enrollment. This is possible for the whole study or a single site.

11.2.1 *Study-wide termination or suspension*

Possible reasons for considering study suspension or termination of the study include but are not limited to:

- Decision by Medtronic or regulatory body (where the study is operating under regulatory body authority)
- Enrollment is slower than anticipated

11.2.2 *Investigator/site termination or suspension*

Possible reasons for clinical investigator or site termination or suspension include but are not limited to:

- Failure to obtain initial Ethics Committee approval or annual renewal of the study
- Persistent non-compliance to the clinical investigation (e.g. failure to adhere to inclusion/exclusion criteria, failure to follow subjects per scheduled follow-ups)
- Lack of enrollment
- Noncompliance to regulations and the terms of the Clinical Trial Agreement (e.g. failure to submit data in a timely manner, failure to follow-up on data queries and monitoring findings in a timely manner)
- Ethics Committee suspension of the site
- Fraud or fraudulent misconduct is discovered (as defined by local law and regulations)
- Investigator request (e.g., no longer able to support the study)

11.3 Procedures for Termination or Suspension

11.3.1 *Medtronic-initiated and regulatory authority-initiated*

- Medtronic will promptly inform the clinical investigators of the termination or suspension and the reasons and inform the regulatory authority(ies) where required
- In the case of study termination or suspension for reasons other than a temporary Ethics Committee approval lapse, the investigator will promptly inform the Ethics Committee and the institution (where required per regulatory requirements)
- In the case of study termination, the investigator must inform the subjects, or legally-authorized designees or guardians and may inform the personal physician of the subjects to ensure appropriate care and follow-up is provided
- In the case of a study suspension, subject enrollment must stop until the suspension is lifted by Medtronic
- In the case of a study suspension, enrolled subjects should continue to be followed out of consideration of their safety, rights and welfare

11.3.2 *Investigator-initiated*

- The investigator will inform Medtronic and provide a detailed written explanation of the termination or suspension
- The investigator will promptly inform the institution (where required per regulatory requirements)
- The investigator will promptly inform the Ethics Committee and regulatory authority (where required per regulatory requirements)
- The investigator will promptly inform the subjects, or legally-authorized designees or guardians and/or the personal physician of the subjects to ensure appropriate care and follow-up is provided
- In the case of a study suspension, subjects enrolled should continue to be followed out of consideration of their safety, rights and welfare

11.3.3 *Ethics committee-initiated*

- The investigator will inform Medtronic and provide a detailed written explanation of the termination or suspension within 5 business days
- Subject enrollment must stop until the suspension is lifted
- Subjects already enrolled should continue to be followed in accordance with Ethics Committee policy or its determination that an overriding safety concern or ethical issue is involved
- The investigator will inform his/her institution (where required per local requirements)
- The investigator will promptly inform the subjects, or legally-authorized designees or guardians and/or the personal physician of the subjects, with the rationale for the study termination or suspension
- The investigator will inform local regulatory authority, where required per regulatory requirements

12 STATISTICAL METHODS AND DATA ANALYSIS

12.1 General considerations

Data analysis will be performed by Medtronic statisticians.

The data will not be analyzed until study completion, which will be approximately two years after the final study enrollment.

Where applicable, missing data is addressed within each objective.

Generally, subjects will be included in their baseline groups in analyses. For example, a subject who is in a primary prevention arm will remain in that arm even if he later falls into the secondary prevention group due to a VT/VF episode. The exception will be subjects who get implanted later in the study. These subjects will be included in the primary endpoint in the group to which they belonged (secondary, 1.5, or 1.0) at the time of implant.

There are 6 study cohorts (see Figure 1 on page 11 for more detail):

- Group A: Secondary prevention subjects implanted with an ICD or CRT-D
- Group B: Secondary prevention subjects not implanted with an ICD or CRT-D
- Group C: Primary prevention subjects who meet 1.5 criteria and are implanted with an ICD or CRT-D
- Group D: Primary prevention subjects who meet 1.5 criteria and are not implanted with an ICD or CRT-D
- Group E: Primary prevention subjects who do not meet 1.5 criteria (1.0 subjects) and are implanted with an ICD or CRT-D
- Group F: Primary prevention subjects who do not meet 1.5 criteria (1.0 subjects) and are not implanted with an ICD or CRT-D

The Statistical Analysis Plan (SAP) is a separate document that will include a comprehensive description of the statistical methods to be included in the final study report and main manuscript. Any change to the data analysis methods described in the CIP will require an amendment only if it changes a principal feature of the protocol. Any other change to the data analysis methods described in the protocol, and the justification for making the change, will be described in the clinical study report.

12.2 Primary Objective #1: Appropriate Therapy

Demonstrate that appropriate VT/VF therapy rates (shock and ATP) for subjects meeting 1.5 prevention criteria implanted with a Medtronic device (ICD/CRT-D) are equivalent (within 30%) to rates in subjects meeting secondary prevention criteria.

12.2.1 Hypothesis

The goal of this hypothesis test is to demonstrate that the overall rate of appropriate VT/VF therapy (shock and ATP) over the observed post-implant time in the study is non-inferior in implanted 1.5 prevention patients compared to implanted secondary prevention patients with a non-inferiority margin of 30%.

H_0 : Hazard ratio of Implanted 1.5 patients to implanted secondary patients ≤ 0.70

H_A : Hazard ratio of Implanted 1.5 patients to implanted secondary patients > 0.70

[figure not shown]
12.2.2 Performance Requirements

The null hypothesis will be rejected if the one-sided 95% lower confidence bound of the hazard ratio of implanted 1.5 subjects to implanted secondary prevention subjects is greater than 0.70.

12.2.3 Rationale for Performance Criteria

Data from the OMNI clinical study was analyzed retrospectively. Figure 2 shows the results, where the hazard ratio between secondary and all primary subjects was 0.76, and the hazard ratio between secondary subjects and the 1.5 subgroup of primary prevention was 0.91. This demonstrates that the 1.5 subgroup may be much more similar to the secondary prevention group than the overall primary prevention group.

Figure 2: Time to First Appropriate VT/VF Therapy in the OMNI Clinical Study

The non-inferiority margin of 30% (corresponding to a hazard ratio of 0.70) was chosen because it is higher than the observed hazard ratio of 1.0 to 1.5 in the OMNI study, which was 0.68. This would demonstrate both that the rate of appropriate VT/VF therapies is similar between 1.5 prevention and secondary prevention patients and that

the 1.5 prevention patients' curve is likely closer to the secondary prevention curve than to the overall primary prevention curve.

In this objective, the direct comparison is only between secondary and 1.5 subjects because it is believed that there will not be enough implanted 1.0 subjects as it is expected that relatively few of these subjects will elect to receive a device.

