12.2.6 Sample Size

A simulation program was written to determine the sample size for the study.

Assumptions are based on the OMNI data and estimates from steering committee physicians:

- 60% of enrollments will be secondary prevention and 40% primary prevention
- 50% of primary subjects will be in the 1.5 group
- 57% of secondary subjects will get an ICD (includes CRT-D)
- 45% of 1.5 subjects will get an ICD
- 22% of 1.0 subjects will get an ICD
- Annual attrition (includes exits and deaths) will be 10%
- The study will end two years after the last enrollment

- 4000 patients will take 2 years to enroll with enrollment beginning slowly, then accelerating to a steady 246 per month.
- Expected rates of appropriately treated VT/VF in secondary subjects follow Figure 2, with a higher rate in the first year (22.5%), then a constant rate (11.1%) thereafter.
- The hazard ratio of 1.5 to secondary is 0.91

Under the above assumptions and using the hypothesis test stated above, 4800 subjects will have 80% power to reject the null hypothesis. With 4800 enrolled patients, it is expected that approximately 1650 secondary prevention subjects will be implanted, 430 1.5 prevention subjects will be implanted, and 200 1.0 subjects will be implanted.

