3.1.3 Reports for which this Statistical Analysis Plan applies

This analysis plan shall apply to the final report. Statistical analysis for study related publications will not be limited to this plan. However, it is the intent that the main study publication will follow the methods detailed in this plan, which in some cases supersede the investigational plan.

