KEEP=HAZARDRATIO HRLOWERCL HRUPPERCL)
LOGRANKAE (WHERE=(TEST='Log-Rank') RENAME=(ProbChiSq=LOGRANKAE) KEEP=TEST
ProbChiSq)
LOGRANKCE (WHERE=(TEST='Log-Rank') RENAME=(ProbChiSq=LOGRANKCE) KEEP=TEST
ProbChiSq)
GROUPN (WHERE=(GROUP='A') RENAME=(COUNT=GROUPA_SS) KEEP=GROUP COUNT)
GROUPN (WHERE=(GROUP='B') RENAME=(COUNT=GROUPB_SS) KEEP=GROUP COUNT)
GROUPN (WHERE=(GROUP='C') RENAME=(COUNT=GROUPC_SS) KEEP=GROUP COUNT)
GROUPN (WHERE=(GROUP='D') RENAME=(COUNT=GROUPD_SS) KEEP=GROUP COUNT)
GROUPN (WHERE=(GROUP='E') RENAME=(COUNT=GROUPE_SS) KEEP=GROUP COUNT)
GROUPN (WHERE=(GROUP='F') RENAME=(COUNT=GROUPF_SS) KEEP=GROUP COUNT)
;

DROP GROUP TEST;
RUN;

%MEND;

```

%% ASSUMPTIONS CAME FROM QUESTIONS ASKED OF 2 CHINESE, 1 INDIAN, AND 1 BELARUSSION PHYSICIANS. THEY WERE ASKED TO ESTIMATE %
 AT THEIR CENTER, THEN IN THE REST OF THEIR COUNTRY. IT IS ASSUMED THAT 1/3 OF THE PTS WILL BE CHINA, 1/3 INDIA, AND 1/3 THE REST.

% OF SECONDARY:
 [name]: 75% HIS CENTER / 75% OTHERS

```

[name]: 70/80
[name]: 50/50
[name]: 30/55
52% CHINA, 78% INDIA, AND 75% ROW = 68%

% OF SECONDARY THAT GET IMPLANTED:
[name]: 98/90
[name]: 80/45
[name]: 50/15
[name]: 50/30
30% CHINA, 50% INDIA, 91% ROW = 57%

% OF 1.5 THAT GET IMPLANTED:
[name]: 65/65
[name]: NO GUESS
[name]: 60/25
[name]: 40/30
30% CHINA, 40% INDIA, 65% ROW = 45%

% OF 1.0 THAT GET IMPLANTED:
[name]: 40/40
[name]: 15/5
[name]: 40/10
[name]: 30/30
20% CHINA, 6% INDIA, 40% ROW = 22%
;

%MACRO LOOP(NUM,SS,PROBSEC,YEARSENROLL,YEARSFOLLOW);
DATA ALLSTUDIES;
RUN;

%DO X = 1 %TO &NUM;
%STUDY(
SS=&SS,
PROBSEC=&PROBSEC,
PROB15=0.5,
IMPSEC=0.57,
IMP15=0.45,
IMPPRIM=0.22,
/*FAIL VARIABLES BELOW WERE CHOSEN TO BEST MATCH THE 12-MONTH FAILURE RATES
AND THE HAZARD RATIOS IN OMNI.  HR OF C TO A WAS 0.909.  HR OF E TO C WAS
0.678*/
FAILA12=0.225,
FAILALONG=0.1110,
HRAC=0.91,
HRCE=0.68,
YEARSENROLL=&YEARSENROLL,
YEARLYATTRITION=0.1,
YEARSFOLLOW=&YEARSFOLLOW);

DATA ALLSTUDIES;
SET ALLSTUDIES STUDYRES;
RUN;
%END;

DATA RESULTS;
SET ALLSTUDIES;

```

```

WHERE FAIL_A12 NE .;

*IF WE WANT STUDY RESULT TO BE THAT C IS CLOSER TO A THAN IT IS TO E;
  *BASED ON DIFFERENCES AT 36 MONTHS.  TOO UNSTABLE TO USE: SOMETIMES
FAIL_E > FAIL_C, YET HR_CE IS STILL <1;
/*      DIFFAC=FAIL_A-FAIL_C; */
/*      DIFFCE=FAIL_C-FAIL_E; */
/*      IF FAIL_E>0 THEN DO; */
/*          IF DIFFCE>DIFFAC THEN OBS_SUCCESS=1; ELSE OBS_SUCCESS=0; */
/*      END; */
/*      ELSE DO; */
/*          IF DIFFAC<0.04 THEN OBS_SUCCESS=1; ELSE OBS_SUCCESS=0;      */

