/*      END; */

IF HR_AC>1 THEN OBS_SUCCESS2=1;
ELSE IF FAIL_E12>0 THEN DO;
  IF HR_AC > HR_CE THEN OBS_SUCCESS2=1; ELSE OBS_SUCCESS2=0;
END;
ELSE DO;
  IF HR_AC> 0.9 THEN OBS_SUCCESS2=1; ELSE OBS_SUCCESS2=0;
END;
LABEL OBS_SUCCESS2='SUCESSFUL TRIAL?  SUCCESS BASICALLY DEFINED AS HR OF
C TO A HIGHER THAN E TO C';

*NON-INFERIORITY TEST - MARGINS OF 20, 25, AND 30%;
  IF HRL_AC>0.7 THEN NONINF70=1; ELSE NONINF70=0;
  IF HRL_AC>0.75 THEN NONINF75=1; ELSE NONINF75=0;
  IF HRL_AC>0.8 THEN NONINF80=1; ELSE NONINF80=0;
  IF HRL_AC>0.85 THEN NONINF85=1; ELSE NONINF85=0;
  IF HRL_AC>0.9 THEN NONINF90=1; ELSE NONINF90=0;

*SUPCESS IF 2.0 IS HIGHER THAN 1.0 AND 1.5 IS HIGHER THAN 1.0;
  IF LOGRANKAE<0.05 AND LOGRANKCE<0.05 AND HR_CE<1 THEN SUPSUCCESS=1;
  ELSE IF LOGRANKAE<0.05 AND HR_AE<1 THEN SUPSUCCESS=0.2;
  ELSE IF LOGRANKCE<0.05 AND HR_CE<1 THEN SUPSUCCESS=0.1;
  ELSE SUPSUCCESS=0;

*OPC SUCCESS;
IF FLCL_C12>0.15 THEN OPC15SUCCESS12=1; ELSE OPC15SUCCESS12=0;
IF FLCL_C24>0.15 THEN OPC15SUCCESS24=1; ELSE OPC15SUCCESS24=0;
IF FLCL_C36>0.15 THEN OPC15SUCCESS36=1; ELSE OPC15SUCCESS36=0;
IF FLCL_C12>0.20 THEN OPC20SUCCESS12=1; ELSE OPC20SUCCESS12=0;
IF FLCL_C24>0.20 THEN OPC20SUCCESS24=1; ELSE OPC20SUCCESS24=0;
IF FLCL_C36>0.20 THEN OPC20SUCCESS36=1; ELSE OPC20SUCCESS36=0;
IF FLCL_C12>0.25 THEN OPC25SUCCESS12=1; ELSE OPC25SUCCESS12=0;
IF FLCL_C24>0.25 THEN OPC25SUCCESS24=1; ELSE OPC25SUCCESS24=0;
IF FLCL_C36>0.25 THEN OPC25SUCCESS36=1; ELSE OPC25SUCCESS36=0;

*NARROW CONFIDENCE INTERVAL SUCCESS;
CIWIDTH12=FUCL_C12-FLCL_C12;
CIWIDTH24=FUCL_C24-FLCL_C24;
CIWIDTH36=FUCL_C36-FLCL_C36;
IF CIWIDTH12<0.05 THEN CI05SUCCESS12=1; ELSE CI05SUCCESS12=0;
IF CIWIDTH24<0.05 THEN CI05SUCCESS24=1; ELSE CI05SUCCESS24=0;
IF CIWIDTH36<0.05 THEN CI05SUCCESS36=1; ELSE CI05SUCCESS36=0;
IF CIWIDTH12<0.08 THEN CI08SUCCESS12=1; ELSE CI08SUCCESS12=0;
IF CIWIDTH24<0.08 THEN CI08SUCCESS24=1; ELSE CI08SUCCESS24=0;

```

```

IF CIWIDTH36<0.08 THEN CI08SUCCESS36=1; ELSE CI08SUCCESS36=0;
IF CIWIDTH12<0.10 THEN CI10SUCCESS12=1; ELSE CI10SUCCESS12=0;
IF CIWIDTH24<0.10 THEN CI10SUCCESS24=1; ELSE CI10SUCCESS24=0;
IF CIWIDTH36<0.10 THEN CI10SUCCESS36=1; ELSE CI10SUCCESS36=0;
IF CIWIDTH12<0.12 THEN CI12SUCCESS12=1; ELSE CI12SUCCESS12=0;
IF CIWIDTH24<0.12 THEN CI12SUCCESS24=1; ELSE CI12SUCCESS24=0;
IF CIWIDTH36<0.12 THEN CI12SUCCESS36=1; ELSE CI12SUCCESS36=0;
IF CIWIDTH12<0.15 THEN CI15SUCCESS12=1; ELSE CI15SUCCESS12=0;
IF CIWIDTH24<0.15 THEN CI15SUCCESS24=1; ELSE CI15SUCCESS24=0;

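### Protocol 12.2.3 credits the 0.70 margin with showing that 1.5 patients are likely closer to secondary than to overall primary prevention, which the primary test cannot show (minor)

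*Protocol*

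**What the plan says.** Protocol 12.2.1 and 12.2.2 and SAP 3.2 define one test. H0 is that the HR of implanted 1.5 to implanted secondary patients is 0.70 or less, and it is rejected if the one-sided 95% lower bound exceeds 0.70.

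Protocol 12.2.3 gives the reasons for the margin. In OMNI, "the hazard ratio between secondary and all primary subjects was 0.76", and the corresponding figure for the 1.5 subgroup was 0.91. The margin was "chosen because it is higher than the observed hazard ratio of 1.0 to 1.5 in the OMNI study, which was 0.68". The section then says that meeting the margin would demonstrate two things: that 1.5 and secondary rates are similar, and that the 1.5 patients' "curve is likely closer to the secondary prevention curve than to the overall primary prevention curve". The next paragraph says that "the direct comparison is only between secondary and 1.5 subjects", because few 1.0 patients are expected to accept a device. Protocol 12.2.6 expects "430 1.5 prevention subjects will be implanted, and 200 1.0 subjects will be implanted".

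**The concern.** The second conclusion is about three groups, but the test compares two. A 1.5 group with the same rate as overall primary prevention would have a true HR of 0.76 to secondary on the section's own figures. That value satisfies the alternative hypothesis, so rejecting H0 cannot rule it out. The 0.68 does not fill the gap, because it compares 1.0 with 1.5 and overall primary prevention includes the 1.5 patients.

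What is at stake is how a positive result is read. Protocol section 2 hopes that the study will help clinicians to identify the highest-risk primary prevention patients and help societies to expand guidelines. A reader of 12.2.3 could take success as evidence that the 1.5 criteria pick out patients nearer to secondary prevention than primary patients in general.

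**Working it through.** **Inputs.** From Protocol 12.2.6 and the SAP Appendix: 4800 enrolled; 60% secondary; 50% of primary patients are 1.5; implant rates 57% (secondary), 45% (1.5) and 22% (1.0); secondary event rates 22.5% in year 1 and 11.1% a year after; attrition 10% a year; accrual 2.24 years plus 2 years of follow-up; HR 0.91; one-sided alpha 0.05. From Protocol 12.2.3: OMNI HRs 0.76, 0.91 and 0.68. The 0.76 is read as primary over secondary, since the SAP's program gives the 1.5-to-secondary ratio as 0.909.

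**1. The plan's own power.** Expected implants are 4800 × 0.6 × 0.57 = 1642 secondary and 4800 × 0.4 × 0.5 × 0.45 = 432 in the 1.5 group. Repeating the SAP Appendix simulation (5000 runs) gives 80.5% power and a mean HR of 0.904. The SAP tabulates 80.4% and 0.903, so the plan's figure reproduces. There are about 663 events, 129 of them in the 1.5 group. The standard error (SE) of the log HR is about 0.098 at the design HR and about 0.104 at a true HR of 0.76.

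**2. Lowest passing estimate.** This is 0.70 × exp(1.645 × SE):
- SE 0.098: 0.70 × exp(0.161) = 0.82
- SE 0.104: 0.70 × exp(0.171) = 0.83

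A just-passing result is still nearer to 0.76 than to 1.00 on the log scale: ln(0.82/0.76) = 0.08 or ln(0.83/0.76) = 0.09, against |ln 0.83| = 0.19 or |ln 0.82| = 0.20. An *observed* 0.76 would fail: its lower bound is 0.76 × exp(−1.645 × 0.104) = 0.64.

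**3. Chance of passing at a true HR of 0.76.** Φ(ln(0.76/0.70)/SE − 1.645):
- SE 0.104: Φ(0.79 − 1.645) = 0.20
- SE 0.098: Φ(0.84 − 1.645) = 0.21

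Two simulations gave 19.0% and 21.1%. At a true HR of 0.70 they gave 5.6% and 4.8%, against a nominal 5%.

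**4. If the true HR is 0.91.** On the log scale, 1.5 is closer to secondary than to overall primary when the 1.5-to-secondary HR exceeds a threshold. The threshold depends on what is held fixed. The last column combines simulation and the normal approximation.

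| What is held fixed | Threshold | Passing estimates above it |
|---|---|---|
| OMNI ratio of overall primary to 1.5 | 0.76/0.91 = 0.835 | 95–98% |
| Overall primary at 0.76 of secondary | √0.76 = 0.872 | 78–82% |
| Expected implant mix, 1.0:1.5 at 0.68 | (430 + 200 × 0.68)/630 = 0.898 | 63–68% |

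Every threshold is above 0.70, so none is secured by rejecting H0.

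**5. Precision of a 1.0-to-1.5 estimate.** With about 46 events in group E and 130 in group C, the SE is about 0.173. If the HR is 0.68, the 95% CI is 0.68 × exp(±1.96 × 0.173) = 0.48 to 0.95.

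**The case against.** The strongest defence is that nothing operative depends on the sentence. It sits in a rationale, is hedged by the word likely, is followed at once by the statement that only secondary and 1.5 are compared, and is not repeated in the hypothesis, the success rule or SAP 3.2. Under the design HR, more than half of passing estimates are closer to secondary on every threshold in step 4. All of this stands, and it keeps the point minor. It does not rescue the claim, because the support for likely comes from assuming 0.91 and not from passing the test.

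The 20% figure can fairly be called selective. The 1.5 patients are part of overall primary prevention, so if they were no different from it, 1.0 and 1.5 would be alike. That keeps OMNI's 0.76 and discards its 0.91 and 0.68. The figure is an illustration, not a forecast.

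A reader might infer from the simulation program that 1.0 was the intended comparator and that the protocol switched it. One comment reads "IF WE WANT STUDY RESULT TO BE THAT C IS CLOSER TO A THAN IT IS TO E", and a success label refers to the HR of "C TO A HIGHER THAN E TO C". The documents do not support that inference. The comment is conditional and heads commented-out code that its author marks as too unstable to use. The label belongs to one of several candidate success definitions. Neither shows where the protocol sentence came from.

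It is also tempting to replace the claim with closeness to secondary rather than to 1.0, since 0.70 exceeds 0.68. That would depend on a ratio this study cannot pin down (step 5). It also depends on the scale: on hazard differences it would need an HR above 1/1.32 = 0.758.

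Finally, SAP 3.2 plans Kaplan-Meier curves for each prevention group, which may include 1.0, and some objectives are redacted. Curves alone give no HR or interval, but redacted text may already provide one.

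**Conclusion.** The concern holds as a minor correction of interpretation. Rejecting H0 shows that the rate in implanted 1.5 patients exceeds 70% of the secondary rate. It does not show that 1.5 is closer to secondary than to overall primary prevention: the true values it allows include 0.76, and an estimate that just passes (0.82 to 0.83) is nearer to 0.76 than to 1.00.

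A reader might infer that the margin or the test is invalid. The documents do not support that: the stated power reproduces, and size at the margin is close to nominal. Nor would an observed HR of 0.76 count as success at the planned size.

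The figures treat OMNI's point estimates as fixed, because the documents give no confidence intervals for them, and they measure closeness on the log-HR scale.

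**What to change.** - Delete the clause about closeness to the secondary rather than the overall primary curve from Protocol 12.2.3 at its next revision. Protocol section 4 requires site-level approval of revisions, so a stand-alone amendment is not worth making.
- State in SAP 3.2 and in the report: *Rejecting H0 shows that the rate of first appropriate VT/VF therapy in implanted 1.5 patients exceeds 70% of the rate in implanted secondary patients; it does not show that 1.5 patients are closer to secondary than to overall primary prevention patients.* SAP 3.1.3 describes its methods as ones "which in some cases supersede the investigational plan". This sentence changes no method, but it keeps the broader claim out of the report.
- Unless redacted text already plans it, report the 1.0-to-1.5 HR (group E to group C) with a two-sided 95% CI, descriptively and without a test.
- Do not add a closeness claim conditional on 0.68.

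The cost is a sentence and one estimate from data already collected, with no alpha spent and no extra patients. The downsides are a narrower claim and an imprecise estimate, made only in patients who accepted an implant.

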12.2.4 Analysis Methods

The hypothesis will be tested using a Cox proportional hazards model with survival time and first appropriate VT/VF episode as the dependent variable and group (secondary or 1.5) as the independent variable. A 95% one-sided lower confidence bound for the hazard ratio and a p-value will also be calculated. The data will be presented in a format similar to the right panel of Figure 2.

Adequate power is needed to perform the hypothesis test. Without adequate power, a non-significant test has little meaning. Therefore, the hypothesis test will not be performed and a p-value will not be calculated if there are fewer than 400 subjects in the implanted 1.5 prevention group. In that case, event rates and confidence intervals will be presented.

Time 0 will be the implant date and subjects will be censored on the date of their latest device interrogation. Only spontaneous, appropriately treated VT/VF episodes as adjudicated by the episode review committee will count toward the endpoint.

VT/VF episodes that cannot be adjudicated (due to not saving full episode data or any other reason) will be ignored. Often, these episodes are followed by episodes that can be adjudicated, and since the endpoint is time to first episode, effects on the results from these events will be minimal. In addition, these should be balanced between the comparison groups.

